### ***Drug-induced liver injury***

The liver function tests, namely AST, ALT, ALP, and total bilirubin, are used to assess possible drug-induced liver toxicity. The proportion of patients with PCSA values at any post-baseline visit by baseline status will be displayed by treatment group for each parameter. The proportion of patients with PCSA values at any post-baseline visit will also be displayed by duration of exposure for each treatment group (only if a tabulation summary is necessary).

Listing of possible Hy's law cases identified by treatment group (eg, patients with any elevated ALT > 3 x ULN, and associated with an increase in bilirubin > 2 x ULN) with ALT, AST, alkaline phosphatase, total bilirubin, and the following complementary parameters (if available): conjugated bilirubin and prothrombin time/international normalized ratio, creatine phosphokinase, serum creatinine, complete blood count, anti-HAV IgM, anti-HBc IgM, anti-HCV and HCV RNA, anti-CMV IgM and anti-HEV IgM antibodies, auto-antibodies: anti-nuclear, anti-DNA, anti-smooth muscle, Epstein-Barr virus, herpes viruses, and anti-LKM.

#### **2.4.5.5 Analyses of vital sign variables**

The summary statistics (including number, mean, median, Q1, Q3, standard deviation, minimum and maximum) of all vital signs variables (HR, SBP, DBP and changes from baseline) will be calculated for each visit or study assessment (baseline, each postbaseline time point, last on-treatment and/or worst on-treatment value and/or other specific assessment) by treatment group. For parameters HR, SBP, and DBP, mean changes from baseline with the corresponding standard error will be plotted over time (at same time points) in each treatment group.

The incidence of PCSAs at any time during the treatment-emergent adverse event period will be summarized by treatment group irrespective of the baseline level and/or according to the following baseline status categories:

- Normal/missing
- Abnormal according to PCSA criterion or criteria

The summaries will include patients in the safety population who have at least 1 assessment performed during the TEAE period. When a PCSA definition involves a change from baseline value, patients must also have a baseline value to be included in the summaries.

A listing of patients with at least 1 post-baseline PCSA will be provided and will display the patient's profile over time of all vital sign parameters. Individual data listings will include the following flags:

- Baseline values will be flagged "B",
- Parameter values reaching a PCSA limit will be flagged (+, or - depending of the direction).

#### **2.4.5.6 Analyses of 12 lead electrocardiogram variables**

The summary statistics (including number, mean, median, Q1, Q3, standard deviation, minimum and maximum) of all 12 lead ECG variables (HR, PR, QRS, QT, QTc and changes from baseline) will be calculated for each applicable visit or study assessment (screening, baseline, postbaseline time points, last on-treatment value) by treatment group. For parameters HR, PR, QRS, QT, QTc mean changes from baseline with the corresponding standard error will be plotted over time (at same time points) in each treatment group.

The incidence of PCSAs at any time during the treatment-emergent adverse event period will be summarized by treatment group irrespective of the baseline level and/or according to the following baseline status categories:

- Normal/missing
- Abnormal according to PCSA criterion or criteria

The summaries will include patients in the safety population who have at least 1 assessment performed during the TEAE period. When a PCSA definition involves a change from baseline value, patients must also have a baseline value to be included in the summaries.

A listing of patients with at least 1 post-baseline PCSA will be provided and will display the patient's profile over time of all vital sign parameters. Individual data listings will include the following flags:

- Baseline values will be flagged "B",
- Parameter values reaching a PCSA limit will be flagged (+, ++, -, or -- depending of the direction and level of the abnormality).

A listing of subjects with at least one abnormality in qualitative assessment (ie, abnormal ECG) during the TEAE will be also provided.

#### **2.4.5.7 24-hours Holter ECG**

The summary statistics (including number, mean, median, Q1, Q3, standard deviation, minimum and maximum) of all Holter ECG variables (24-hour average and night time average heart rate, and changes from baseline) will be calculated for each applicable visit or study assessment (screening, baseline, postbaseline time points, last on-treatment value) by treatment group. For parameters 24-hour average and night time average heart rate, mean changes from baseline with the corresponding standard error will be plotted over time (at same time points) in each treatment group.

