### 1.2.2 Secondary objectives

#### Main secondary objectives:

- To assess the effect of once daily dosing of SAR425899 on body weight over 26 weeks.
- To assess the safety and immunogenicity profile of SAR425899 when administered as daily subcutaneous (SC) injections over 26 weeks, including assessment of the heart rate (HR) change from baseline to Week 26 by electrocardiogram (ECG) and Holter monitor.

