#### 2.1.4 Safety endpoints

The safety endpoints are assessed by:

- Adverse events (AEs), serious adverse events (SAEs), AE of special interest (AESIs), hypoglycemia (severe, documented, asymptomatic, probable, relative), vital signs, ECG changes, and safety laboratory values,
- Change of heart rate from baseline to Week 26 by ECG,
- Change of heart rate from baseline to Week 26 by Holter monitor in up to 50% subset of all patients,
- Antibody assessments: anti-SAR425899 antibodies samples will be collected in all patients (except patients on Liraglutide) at baseline, Week 2, Week 4, Week 14, and Week 26 before dosing. Patients will be asked to provide sample for anti-SAR425899 antibodies assessments 3 months after the end of the study if needed.

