### *General common rules*

All safety analyses will be performed on the safety population as defined in [Section 2.3.2](#), unless otherwise specified, using the following common rules:

- Safety data in patients who do not belong to the safety population (eg, exposed but not randomized) will be listed separately;
- The baseline value is defined as the last available value before the first injection of IMP.
- The PCSA values are defined as abnormal values considered medically important by the Sponsor according to predefined criteria/thresholds based on literature review and defined by the Sponsor for clinical laboratory tests, vital signs, and ECG (PCSA version dated May 2014 [[Appendix A](#)]).
- PCSA criteria will determine which patients had at least 1 PCSA during the TEAE period, taking into account all evaluations performed during the TEAE period, including unscheduled or repeated evaluations. The number of all such patients will be the numerator for the treatment-emergent PCSA percentage;
- The treatment-emergent PCSA denominator by group for a given parameter will be based on the number of patients assessed for that given parameter during the TEAE period by treatment group in the safety population;
- For laboratory parameters cited in the protocol as efficacy endpoints (including HbA1c and plasma glucose), PCSA summaries will not be provided. These parameters will be summarized in [Section 2.4.4](#);
- For quantitative safety parameters based on central laboratory/reading measurements, descriptive statistics will be used to summarize results and change from baseline values by visit and treatment group. Summaries will include the last on-treatment value (see [Section 2.4.5.4](#));
- The analysis of the safety variables will be essentially descriptive and no systematic testing is planned. Relative risks versus placebo and their 95% CIs may be provided, if relevant;
- Selected safety analyses will be summarized by age group (<50, ≥50 to <65, ≥65 to <75, ≥75 years of age), gender, race subgroups, and any pertinent subgroups as appropriate (see details in [Section 2.4.5.1](#) and [Section 2.4.5.2](#)).

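### Heart-rate change is named within a main secondary safety objective, but the SAP body gives no baseline-adjusted dose-minus-placebo difference with an interval

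*SAP*

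**What the plan says.** Under "Main secondary objectives", SAP 1.2.2 (matching protocol 5.2) sets a safety and immunogenicity objective, "including assessment of the heart rate (HR) change from baseline to Week 26 by electrocardiogram (ECG) and Holter monitor". SAP 2.1.4 then lists two separate endpoints: "Change of heart rate from baseline to Week 26 by ECG" and "Change of heart rate from baseline to Week 26 by Holter monitor in up to 50% subset of all patients".

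The planned analyses are:

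- **12-lead ECG (SAP 2.4.5.6):** summary statistics of "all 12 lead ECG variables (HR, PR, QRS, QT, QTc and changes from baseline) will be calculated for each applicable visit", by treatment group, with mean-change plots and PCSA incidence.
- **Holter (SAP 2.4.5.7):** summary statistics by treatment group for "24-hour average and night time average heart rate, and changes from baseline". In addition, "mean changes from baseline with the corresponding standard error will be plotted over time (at same time points) in each treatment group".
- **Vital signs (SAP 2.4.5.5):** the same kind of summary for supine heart rate, with PCSA incidence.
- **Elsewhere:** AESI counts that include persistent sinus tachycardia (SAP 2.1.4.2 and Analysis of AESI), and exploratory PK/heart-rate modelling (SAP 1.2.3 and 3).

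The general rule in SAP 2.4.5 is: "The analysis of the safety variables will be essentially descriptive and no systematic testing is planned". The only between-group safety statistic it mentions is an optional relative risk against placebo with a 95% CI.

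By contrast, SAP 2.4.4.2 and 2.4.9.1 give continuous efficacy endpoints and the questionnaires an ANCOVA difference from placebo with a 95% CI.

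**The concern.** The placebo group is there to separate a drug effect on heart rate from regression to the mean and visit effects. That calls for the difference from placebo and its uncertainty. The plan tabulates the ingredients arm by arm but does not plan the contrast. It also leaves baseline heart rate, which is collected in every patient by ECG and in the Holter subset by Holter, out of any adjustment.

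The ordering is odd. The questionnaires serve an exploratory objective and get an adjusted difference with an interval. Heart rate is named in a higher-ranked objective and gets none.

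Group size makes this matter. Placebo has 30 patients in total, and about 15 with Holter if the subset reaches its cap and is spread evenly. With so few, a reader comparing five arm means may see a dose effect that is noise, or miss one that is there.

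**Working it through.** **The plan's own figure first.** Protocol 11.1 states 80% power for HbA1c with 60 v 30 patients, a difference of 0.7%, SD 1.1% and two-sided 5%.

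- SE = 1.1 × √(1/60 + 1/30) = 0.246, and 0.7/0.246 = 2.85.
- Power is 81.2% by the normal approximation and 80.4% by the noncentral t with 88 df.

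The statement reproduces and is not in question. It covers HbA1c only; no power or SD is given for heart rate.

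**Precision of a heart-rate contrast.** Inputs:

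- 60 per dose and 30 pooled placebo (protocol 11.1).
- Holter limited to the first patients who agree, up to 50% (SAP 2.1.4.8). An even spread, assumed here, gives 30 per dose and 15 on placebo.
- No dropout (assumed).

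Half-width of the 95% CI = t(0.975, n₁+n₂−2) × SD × √(1/n₁ + 1/n₂).

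- ECG, 60 v 30: √0.05 = 0.224; times t on 88 df gives 0.444 SD.
- Holter, 30 v 15: √0.1 = 0.316; times t on 43 df gives 0.638 SD.

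The documents give no SD for heart-rate change, so the bpm values below rest on an assumed range:

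| Assumed SD of change (bpm) | ECG half-width (bpm) | Holter half-width (bpm) |
|---|---|---|
| 6 | 2.7 | 3.8 |
| 8 | 3.6 | 5.1 |
| 10 | 4.4 | 6.4 |
| 12 | 5.3 | 7.7 |

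**Gain from baseline adjustment.** With equal variances at baseline and Week 26 and correlation r between them, the ratio of ANCOVA to change-score variance is (1−r²)/(2(1−r)) = (1+r)/2.

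- r = 0.5: variance ratio 0.75, width ratio √0.75 = 0.866, so about 13% narrower.
- r = 0.7: variance ratio 0.85, width ratio √0.85 = 0.922, so about 8% narrower.

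These correlations are also assumed. On the ECG interval at SD 8-10 bpm, the gain runs from 3.6 × 0.078 ≈ 0.3 bpm to 4.4 × 0.134 ≈ 0.6 bpm.

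**Which groups to compare.** SAP 2.3.2 places a SAR425899 patient in the dose received from the Week 8 visit, and protocol 8.1.1 lets patients who cannot tolerate the target dose stay on a lower one. The planned safety groups can therefore differ from the randomised groups for a reason linked to the drug. SAP 2.5.4 also limits the by-visit safety statistics to the TEAE period, which drops later values from patients who stopped treatment. A difference from placebo computed on those groups would not be a randomised contrast.

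**The case against.** The strongest reply is that descriptive safety analysis is a stated choice, made consistently in the protocol and the SAP for a Phase 2 trial sized on HbA1c. That stands. A reader might infer that the plan contradicts its own objective; it does not, because assessing heart rate does not promise a between-group estimate.

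A reader might also infer that heart rate is a main secondary objective in its own right, or that the plan offers nothing beyond arm means and SDs. Neither is supported. Heart rate is one clause of a broader safety and immunogenicity objective. The plan also provides standard-error plots for every arm including placebo, PCSA incidence for ECG and vital signs, tachycardia AESI counts and PK/heart-rate modelling.

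Nor is imprecision hidden altogether. Placebo change is shown beside each dose, and an unadjusted difference and interval can be worked out from each arm's N, mean and SD. What the tables cannot yield is the baseline-adjusted contrast, or any contrast in the groups as randomised where patients have changed dose group.

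The ban on systematic testing does not bar an estimate. An interval needs no alpha allocation, and the same rule already allows intervals against placebo for relative risks.

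**Conclusion.** The point holds as a cheap improvement, not as an error in a stated rule. In the supplied SAP body, heart-rate change has no planned baseline-adjusted difference from placebo with an interval, although lower-ranked outcomes do.

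The SD-unit half-widths (0.44 for ECG, 0.64 for Holter) assume full follow-up and, for Holter, an even split at the 50% cap. The bpm figures also need the assumed SD, and the 8-13% narrowing needs the assumed correlation. Dropout or fewer placebo Holter patients would widen the intervals. These figures describe how precise the missing estimate would be. They do not show bias or a changed conclusion.

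One limit applies: SAP Appendix B, the summary of statistical analyses, was not in the supplied text.

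**What to change.** Add to SAP 2.4.5.6 and 2.4.5.7 an ANCOVA of heart-rate change from baseline to Week 26, with treatment group and baseline heart rate as terms. Fit it separately for 12-lead ECG heart rate, the Holter 24-hour mean and the Holter night-time mean.

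- **Population:** treated patients grouped as randomised, with the three placebo arms pooled. Keep the by-dose-received summaries as planned.
- **Report:** each dose minus placebo with a 95% CI, labelled as estimation, with no test and no multiplicity claim.
- **State:** that restricting to on-treatment values conditions on tolerability, and how many patients per randomised arm contribute.

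The cost is two extra tables from data already collected. The downside is that the intervals will be wide, especially for Holter, and the text should say so.

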#### **2.4.5.8 Analyses of anti-drug antibody variables**

Analyses of antibody variables will be performed on the safety population (only in patients from SAR treatment groups).

The number and percentage of patients by antibody status will be listed and summarized by visit, as well as the percentage of conversion from negative to positive status from baseline to Week 26.

Antibody levels (titer or concentration) will be listed and summarized by visit using descriptive statistics by N, geometric mean, coefficient of variation, median, minimum and maximum.

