9.2.2.7 Anti-SAR425899 antibody assessment

Anti-SAR425899 antibody samples will be collected in all patients (not for patients in the liraglutide arm) at baseline, Week 2, Week 4, Week 14, and Week 26 before dosing. Patients will be asked to provide sample for anti-SAR425899 antibodies assessments 3 months after the end of the study if needed. As immunogenicity might contribute to patient safety, it is important for an ADA-assay intended to be used for clinical trials to achieve the highest sensitivity. Therefore, a 3-tiered approach will be employed to evaluate immunogenicity of SAR425899 in a clinical setting. In the first tier, all samples will be screened in order to distinguish putative positive

samples from negative samples. Identified putative positive samples will be re-tested in the confirmatory assay in tier 2 where specific ADAs are identified. All confirmed anti-SAR425899 positive samples from tier 2 will be further characterized in tier 3. These samples will be titrated and ADAs cross-reacting with endogenous human Glucagon and GLP1 will be identified. In order to assess the neutralizing capacity of confirmed anti-SAR425899 positive ADA samples, dedicated anti-SAR425899 neutralizing assays will be employed.

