11.4.3.6 Analyses of antidrug antibody variables

Analyses of antibody variables will be performed on the safety population (only in patients from SAR treatment arms).

The number and percentage of patients by antibody status will be listed and summarized by treatment group and visit, as well as the percentage of conversion from negative to positive status from baseline to Week 26.

Antibody levels (titer or concentration) will be listed and summarized by treatment group and visit using descriptive statistics by N, geometric mean, coefficient of variation, median, minimum and maximum.

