#### **2.1.4.9 Anti-SAR425899 antibody assessment**

Anti-SAR425899 antibody status (Positive, Negative), antibody levels (titer or concentration) will be collected on the safety population and only in patients from SAR treatment groups.

The TEAE period for antibody variables is defined in [Section 2.1.4](#).

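### Placebo patients are sampled for anti-SAR425899 antibodies but left out of the antibody analysis, so no concurrent post-baseline placebo rate is reported

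*SAP*

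**What the plan says.** - **Who is sampled.** SAP 2.1.4: "anti-SAR425899 antibodies samples will be collected in all patients (except patients on Liraglutide) at baseline, Week 2, Week 4, Week 14, and Week 26". Protocol 9.2.2.7 agrees: "Anti-SAR425899 antibody samples will be collected in all patients (not for patients in the liraglutide arm". The flow chart excludes only the liraglutide arm. Placebo patients are therefore sampled five times, once before dosing and four times after.
- **Who is analyzed.** SAP 2.4.5.8: "Analyses of antibody variables will be performed on the safety population (only in patients from SAR treatment groups". Protocol 11.4.3.6 carries the same limit: "only in patients from SAR treatment arms".
- **A conflicting statement on collection.** SAP 2.1.4.9 says that antibody status and level "will be collected on the safety population and only in patients from SAR treatment groups".
- **What is reported.** SAP 2.4.5.8: "The number and percentage of patients by antibody status will be listed and summarized by visit". It adds the share of patients who convert from negative to positive between baseline and Week 26. Protocol 11.4.3.6 asks for status by treatment group as well as by visit. The SAP text names only the visit.
- **The assay.** Protocol 9.2.2.7 reasons that "it is important for an ADA-assay intended to be used for clinical trials to achieve the highest sensitivity", and then sets out three tiers: screening, confirmation, and characterization of confirmed positives.
- **Other uses of antibody status.** SAP 2.4.5.1 splits hypoglycemia by antibody status and counts a patient as positive after a single positive result at any time in the treatment-emergent period. SAP 2.4.5.2 splits common adverse events by antibody status for the SAR425899 groups.

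**The concern.** Immunogenicity is part of a main secondary objective (Protocol 5.2, SAP 1.2.2), and conversion from negative to positive is its main summary. To attribute conversion to the drug, a reader wants to know how often patients who never received it convert when tested on the same schedule with the same assay. The randomized, blinded placebo group is the only such comparison in the trial. The plan takes its samples but omits them from the antibody tables.

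At stake is the reading of a low conversion rate on SAR425899. If a few percent convert, the report as planned will not show whether placebo patients did the same. The primary endpoint is not affected, and no test or decision rule depends on the antibody tables.

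**Working it through.** The documents state no antibody rate, assay false-positive rate or antibody-based sample size, so there is no planned figure to reproduce. The check is one of text, with an illustration of size.

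**1. The sections side by side.** SAP 2.1.4 and Protocol 9.2.2.7 sample everyone except liraglutide patients. SAP 2.1.4.9 says the data come only from the SAR groups. Both cannot hold. The term for the SAR groups is not defined, and SAP 1.1 calls the placebo arms SAR425899 placebo arms. However, SAP 1.1 lists active and placebo arms separately, so active arms only is the natural reading.

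**2. Samples concerned.** Planned placebo patients 3 × 10 = 30; visits 5; 30 × 5 = 150 samples at most.

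**3. What the planned tables show.** By-visit status in SAR425899 patients includes baseline, so a pre-dose rate in up to 3 × 60 = 180 patients is available. Conversion starts from a negative baseline, which removes baseline positives. The antibody section provides no placebo result at Weeks 2, 4, 14 or 26. SAP 2.4.5.1 does not name the groups for its antibody split, but it relies on a variable that SAP 2.1.4.9 confines to SAR groups, so it cannot be counted on to supply one.

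**4. Size under assumed rates.** Let p be the chance that a sample from a truly negative patient is still positive after confirmation. The documents do not give p, so 0.5%, 1% and 2% are assumed. Samples are taken as independent, with all 180 patients tested at every visit.

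- False conversion, negative at baseline and positive at Week 26: 180 × p × (1 − p).
- False positive at one or more of the four post-baseline visits: 180 × [1 − (1 − p)^4].

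| p | Week 26 conversion, of 180 | Any of 4 visits, % of patients | Any of 4 visits, of 180 |
|---|---|---|---|
| 0.5% | 0.9 | 2.0% | 3.6 |
| 1% | 1.8 | 3.9% | 7.1 |
| 2% | 3.5 | 7.8% | 14.0 |

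The Week 26 column fits the natural reading of conversion in SAP 2.4.5.8, which compares two time points. The any-visit columns fit the any-time definition in SAP 2.4.5.1, which has no baseline condition.

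**5. What a placebo column could show.** At the same rates, the expected number of the 30 placebo patients positive at any of the four visits is 0.6, 1.2 or 2.3, and the chance of seeing at least one is 45%, 70% or 91%. Exact 95% intervals: 0/30 gives 0 to 11.6%, 1/30 gives 0.1 to 17.2%, and 2/30 gives 0.8 to 22.1%. For comparison, a baseline result of 0/180 gives 0 to 2.0%.

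**The case against.** The strongest defense is that the plan already has two safeguards. Baseline status in up to 180 SAR425899 patients is a treatment-naive rate and is far more precise than anything 30 placebo patients can give. Screen positives must also pass a confirmatory assay, which exists because the first tier is tuned for sensitivity. The safety analyses are essentially descriptive, so the missing column changes no inference.

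Much of this stands, and it rules out three stronger readings.

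- A reader might infer that no background rate is shown at all. The by-visit baseline summary shows one.
- A reader might infer that assay false positives simply count as immunogenicity. Only those that survive confirmation could, and their rate is not stated.
- A reader might take the mention of cross-reactivity with glucagon and GLP-1 to mean that positives in unexposed patients must be expected. In Protocol 9.2.2.7 cross-reactivity is characterized in the third tier, in samples already confirmed positive, and nothing there says it produces positives.

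The defense does not supply a concurrent rate. Baseline is one test per patient before treatment. It cannot show how positives accumulate over four later tests, or a change over time unrelated to the drug.

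**Conclusion.** The point holds in a limited form. Placebo patients are sampled after baseline, both documents exclude them from the antibody analysis, and SAP 2.1.4.9 contradicts SAP 2.1.4 on whether their data are collected. What is missing is the concurrent post-baseline placebo rate, and nothing broader.

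The size depends on an assay rate that the documents do not give. At an assumed 0.5% to 2% per sample, false converters at Week 26 number about 1 to 4 of 180. The larger figures of about 4, 7 or 14 apply only to positivity at any of the four visits. A reader might take them as the number of false converters, but conversion from baseline to Week 26, read as two time points, does not support that. Both sets assume independent samples. Interference that persists within a patient would lower the any-visit figures, and would tend to appear at baseline and so drop out of conversion.

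This is a minor, inexpensive improvement to a descriptive safety summary.

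**What to change.** 1. In SAP 2.1.4.9, SAP 2.4.5.8 and Protocol 11.4.3.6, replace the restriction with: SAR425899 groups and pooled placebo. Changing the SAP alone would create a new mismatch with the protocol.
2. Reconcile SAP 2.1.4.9 with SAP 2.1.4 and Protocol 9.2.2.7 on who provides samples.
3. Tabulate status by visit, and conversion, by treatment group, restoring the split that Protocol 11.4.3.6 already asks for.
4. State whether conversion means positive at Week 26 or at any post-baseline visit.

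The cost is one column in tables already planned, plus assaying any placebo samples not yet run (150 at most). The return is modest: 30 patients give a coarse rate, so the placebo column should be read with its interval and beside the baseline rate in SAR425899 patients.
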